9. Wheelchair bound, uses a cane or walker, or unable to carry out physical activity, including walking, due to a chronic disability or documented medical condition.

Intervention

MyROAD is a card that has been designed by CC innovators and American Greetings. When the card is opened, there is a general message that is automatically played. Within the card is a heart shaped cutout that has 4 buttons, one in each quadrant. When pressed, each button has audio of one aspect of general HF education: diet, medications, signs and symptoms of worsening condition and physical activity. The buttons can be pressed as desired (for approximately 2 weeks, until the battery expires) to allow playback of messages. At the top of the heart is a space for the phone number of who to call with questions. CCF Marketing and Brand team has been involved in card art and wording including, color choices, formatting, designs and branding/logos. A magnet allows the heart to adhere to metal surfaces as a visual reminder of self-care; see [Appendix A](#). The script was developed by a HF expert clinician ([name]) and reviewed and approved by [name], vice chair of Cardiology and section head of Heart Failure and Cardiac Transplantation in the Heart and Vascular Institute; see [Appendix B](#). The speaker of the script is a professional radio voice (hired by American Greetings). The card material can be written on, as desired by a health care provider; for example, a nurse can write down the specific dietary sodium limit/day or a phone number. The HF discharge instructions are short, global versions of discharge instructions used by Cleveland Clinic and match current global discharge instruction messages on self-care found in our HF Handbook and HF zones sheet, used by all CC hospitals in Northeast OH.

Outcomes and Measurement

Case report forms will be used to collect all-cause and HF hospitalization, ED visit, and death (or cardiac transplantation or VAD) healthcare consumption and also, 7-day adherence to the scheduled post-discharge follow-up appointment.

- Data will be collected at baseline and 45-, 90-, and 180-day days after discharge

Quality of life will be measured using the *Kansas City Cardiomyopathy Questionnaire* (KCCQ). Kansas City Cardiomyopathy Questionnaire (KCCQ) is a 23 item questionnaire that measures

V1_01-20-16

NCT02901314

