physical limitations, symptoms, self-efficacy, social interference and quality of life.^{18, 19} KCCQ is valid, reliable and a responsive health measure.¹⁸ When 2 generic QOL tools were compared to KCCQ at baseline and 6 weeks for clinical changes, the KCCQ outperformed the 2 generic tools (EQ-5D and Rand 12).¹⁹ Ultimately, a mean change in score by 4.5 points (higher or lower) at 6 weeks reflected a change by 1 New York Heart Association functional class for overall summary score and a mean change in score by 5 points (higher or lower) at 6 weeks reflected a change by 1 New York Heart Association functional class for clinical summary score.¹⁹ Further, in previous research conducted at Cleveland Clinic in a study of patients with HF and similar enrollment criteria, the KCCQ was highly sensitive to changes in 60-day HF-related QOL between usual care and a 1-liter fluid restriction groups.²⁰

- Data will be collected at baseline and 45 days after discharge

Symptoms will be measured using a case report form that contains a list of commonly reported symptoms. Patients would place a check mark in the box of symptoms they have had in the last 7 days. This tool is essentially 1 item and should take about 30-60 seconds to complete. The tool has been used in previous research by the principal investigator and in analysis, patient perceptions of many signs and symptoms were highly associated with functional status and hospitalization.

- Data will be collected at baseline and 45 days after discharge

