Perceived adherence to activity/exercise recommendations will be measured using an investigator-developed form that is an extension of the physical activity and exercise case report form used in the 2009 exercise study conducted by the PI. The modified PACE tool is a 1-item tool with 17 response options that requires patients to select the option that reflects the highest level of purposeful walking, or moderate or vigorous exercise. The original PACE tool had 11 response options and focused only on moderate to vigorous exercise.

- Data will be collected at baseline and 45 days after discharge

Case report forms will be used to collect patient characteristics and medical history at baseline. The *Charlson Comorbidity Index* will be used to collect medical history. This index was developed to classify comorbid conditions which might change the risk of mortality.²⁵⁻³⁰ The score will be categorized into 3 groups (score of 1-2 = 1; 3-4 = 3; 5 or more = 5). In one study with 33,940 patients with ischemic heart disease, the grouping demonstrated a strong relationship with mortality rate.³⁰ This data will also be used to describe the sample groups for similarity in acuity.

- Data will be collected at baseline.

Data Collection

Medical records will be assessed for inclusion and exclusion criteria before approaching patients. Research personnel will explain the study in a patient's room (private in the J building and with the room-separating curtain closed when a double room on Main campus or at Hillcrest or Fairview Hospitals). After received verbal informed consent, patients will complete baseline data. After completing baseline paperwork, patients will be randomly assigned to the usual care or usual care plus MyROAD card group using block randomization; with blocks of 20 to decrease the influence of external factors that could alter outcomes. The randomization assignment will be made by a QHS statistician.

After randomization to groups:

- Intervention group patients will receive the MyROAD card by research personnel. The card can be administered at the time of enrollment, there is no need to wait till day of discharge, since voice-recorded messages are standard care and are not individualized. Patients will also be instructed that their healthcare providers (including their nurse caregivers) will deliver usual care discharge instructions and patient education.

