The main campus of Cleveland Clinic has a high volume of HF discharges each year. Fairview and Hillcrest Hospitals have moderate volumes of HF discharges, and are less likely to have patients who meet exclusion criteria due to enrollment in another research study or advanced HF. Electronic medical records allow for review of data on events that occur in *all* system hospitals and regional medical practice ambulatory care sites; decreasing the need to rely on patient recall of rehospitalization and emergency care events.

The MyCard instructions are a global representation of standard HF discharge instructions found in written handouts and other sources of patient education (videos, verbal instructions from healthcare providers). No new information is presented; thus, the MyRoad card is an extension of usual care delivered in a *different format that is repeatable*. Patients do not need to be able to

read and if they are forgetful, they can replay messages multiple times before the battery cycle ends (around 2 weeks of frequent use).

Nurse managers, clinical nursing directors and cardiologist medical directors of each hospital involved (7th floor J building and general medical units of main campus; multiple medical units of Hillcrest and Fairview Hospital—however, patients with HF are concentrated on PK2-Progressive Care Unit [Fairview Hospital] and 5M [Hillcrest Hospital] are aware that this study will be starting and agreed (and were actually excited) that we are included their patients/units. Research personnel from the Office of Nursing Research and Innovation will be involved in recruitment and all data collection. The main campus has multiple research projects in place. My team is accustomed to working with cardiology research nurses to ensure patients are not approached for more than 1 research study.

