Self- or research nurse-administered instruments that will be completed at baseline, 45, 90 and 180-days are short, simple and will be quick to complete. Patients may become fatigued when completing data collection forms; however, there are only 5 forms for patients to complete at baseline (quality of life, symptoms, functional status, physical activity/exercise and a case report form of demographic information); all of which are short (most are single page) and should not take more than 10 minutes to complete. The 4 forms used at 45 days should take no more than 5 minutes to complete. We have used all instruments in previous research and do not anticipate a burden to patients who enroll. There is only a telephone call at 90- and 180-days. Data obtained from electronic medical records is consistently present, minimizing the occurrence of missing data.

Limitations and Anticipated Problems

Patients and caregivers may never listen to the recorded message after discharge, or loose, throw out or misplace the card. Patients may hear, but ignore, message content. Patients may drop out before the 180-day follow-up data collection. Patients in both groups may ignore self-monitoring and self-care messages based on past practices, implicit beliefs about how to monitor and care for self or misperceptions of family or friends. Analyses will be completed using “intent to treat” methods. In this way, we will be able to learn the effect size of the intervention among all patients randomized to the intervention group.

No adverse effects are anticipated, as the intervention in this research is a greeting-type card that cannot create harm to patients. The audio script provides global messages of content used in usual care education and discharge instruction materials. There are no risks of adverse events from the intervention itself.

Human Subjects Protection

Approval by the Cleveland Clinic Institutional Review Board will be sought prior to study initiation. We believe this study is minimal risk as the intervention is a greeting-type card that repeats self-care monitoring and instruction messages that are part of usual heart failure post-discharge care.

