Appendix B. Audio Script

CLEVELAND CLINIC – MY ROAD CARD

Script for American Greetings – Heart Failure

INTRO (plays audio when the card is opened)

Cleveland Clinic cares about you and your health, so we've designed this message to help you take the best care of yourself after leaving the hospital. The messages in this card will cover important information regarding physical activity, diet, medication, and self-monitoring. Your primary medical diagnosis is heart failure. Heart failure is a chronic condition. It is important to take actions to improve your health and stabilize heart failure. Contact your doctor if you still have questions after hearing and carrying out the actions provided in this card.

PHYSICAL ACTIVITY (Plays when the physical activity button is pressed)

Physical activity is extremely important for you. Start slow with walking 10 minutes a day. Over the course of a month, build up to walking 30 minutes a day. Do not worry if you feel short of breath or have a fast heart rate as you engage in physical activity – this is all normal.

Unless your doctor or nurse specifically advised against walking or completing other physical activities you should be active 5 days per week. If you feel ready for more activity beyond walking, you can try swimming, bicycling, or walking briskly.

DIET (Plays when the diet button is pressed)

Eat fresh foods as much as possible. Do not take in more than 2900 mg of sodium per day. Avoid eating frozen, boxed, bagged, or canned foods. The 6 most salty foods are breads, soups, breaded meats, pizza, deli meats and deli sandwiches. Please avoid these salty foods. Limit the use of butter and ask your server about sodium content if you eat at a restaurant. Read food labels for sodium content and serving size to learn if you are taking in too much sodium.

MEDICATIONS (Plays when the medications button is pressed)

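### The protocol rules out any risk from the card, but it does not dedicate any capture to non-serious or activity-related harms during playback and build-up, and does not plan to read its serious-event data as safety data.

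*Combined protocol and SAP*

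**What the plan says.** **Risk.** Limitations and Anticipated Problems states "No adverse effects are anticipated, as the intervention in this research is a greeting-type card that cannot create harm to patients" and then "There are no risks of adverse events from the intervention itself". Human Subjects Protection uses milder language and calls the study minimal risk.

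**Exposure.** Under Intervention, the buttons work "for approximately 2 weeks, until the battery expires". Feasibility ties the same two weeks to frequent use. Data Collection adds that "The card can be administered at the time of enrollment, there is no need to wait till day of discharge". The Physical Activity message in Appendix B says "Over the course of a month, build up to walking 30 minutes a day", then sets a target of five active days a week and offers more demanding activities to those who feel ready.

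**Patient-reported data.** The three telephone calls match days 45, 90 and 180. Symptoms are recorded at baseline and day 45 on a checklist: "Patients would place a check mark in the box of symptoms they have had in the last 7 days". The Kansas City questionnaire, which has symptom scales, is also given at baseline and day 45; the protocol states no recall period for it. The forms listed for mailing to patients who cannot be reached do not include the symptom checklist.

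**Serious events.** All-cause and HF hospitalization, ED visits and death (or transplant or assist device) are collected in both arms, from the electronic record, telephone contact and mailed forms. Analyses covers a 6-month composite of death or readmission, readmission rates and time to first readmission. It plans no analysis of ED visits and no comparison for harm.

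**The concern.** The trial expects the card to change symptoms, function, activity, hospital use and death. An intervention expected to move these outcomes could move them in either direction, so absence of risk is an assumption here and not a finding.

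The population is NYHA class III or ambulatory IV, just hospitalized for decompensation. The Introduction reports that activity instruction ranks lowest in nurses' comfort and frequency of teaching, and that patients may therefore not receive it. On the protocol's own account, the card may deliver activity advice that usual care leaves out.

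Appendix B also contains two messages that need reconciling. Physical Activity tells patients not to be concerned about breathlessness or a rapid heart rate during activity. Self-Monitoring lists new or worsening breathlessness as a reason to call. How they should read together is for the sponsor to settle, but a flat denial of risk is harder to defend beside them.

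At stake is the safety statement in the eventual report. A fall, near-faint or exertional symptom in the first month that leads to no admission or ED visit has no dedicated route into the data. The serious events that are recorded would be reported only as efficacy.

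**Working it through.** The plan states no figure for harm, so there is none to reproduce. Two checks apply.

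**1. Timing (days from discharge, card given at discharge)**

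| Item | Source | Days |
|---|---|---|
| Playback | Intervention; Feasibility | about 0–14 with frequent use |
| Walking build-up | Appendix B | about 0–30 |
| Day-45 checklist recall | Outcomes and Measurement | 45 − 7 = 38 to 45 |

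The recall window opens 38 − 14 = 24 days after playback ends and 38 − 30 = 8 days after build-up ends. A card given before discharge lengthens the first gap; light use may shorten it.

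**2. What the serious-event data can show**

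*Formula check.* For n per arm, usual-care risk p₁, card risk p₂ and mean risk p̄, with pooled variance and no continuity correction:

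power = Φ{ [ |p₂ − p₁|√n − z√(2p̄(1 − p̄)) ] / √(p₁(1 − p₁) + p₂(1 − p₂)) }

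With the plan's one-sided 0.05 and 80% power, this method returns its 734 (25% vs 17.5%) and 468 (35% vs 24.5%). For 18% vs 12.6% it returns 1098 where the plan has 968; 968 comes from 20% vs 14%. That mismatch is a separate matter and does not affect this point.

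*Events by day 14 (assumption: constant hazard to day 30).* 1 − 0.82^(14/30) = 8.8% of usual-care patients are readmitted. Against the 35% expected at 180 days, that is 8.8/35 = 25%. If every 30-day readmission fell by day 14, the share would be at most 18/35 = 51%. A 180-day comparison therefore mixes the playback period with a much longer one.

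*Expected usual-care readmissions.* With 484 evaluable per arm (968/2): 484 × 0.088 ≈ 43 by day 14 and 484 × 0.18 ≈ 87 by day 30. With 234 per arm (468/2): about 21 and 42. Early tables would not be empty.

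*Power for a 30% relative increase.* This mirrors the plan's benefit effect, with a two-sided 0.05 test (z = 1.96). Example for 18% vs 23.4%, n = 484: p̄ = 0.207; numerator 0.054 × 22 − 1.96 × 0.573 = 0.065; denominator 0.572; Φ(0.114) = 0.545.

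| Usual-care risk | 468 evaluable | 968 evaluable |
|---|---|---|
| 8.8% (day 14, assumed) | 16% | 28% |
| 18% (day 30) | 30% | 55% |
| 35% (day 180) | 64% | 92% |

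With 968 evaluable, the smallest increase detectable at 80% power is a risk ratio of about 1.41 at 18% risk and 1.25 at 35%. With 468 it is about 1.61 and 1.36.

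The sample size rests on one-sided tests for benefit, and Analyses does not state sidedness. A one-sided test for benefit would not register an excess in the card arm.

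**The case against.** The strongest reply is that the main safety data already exist. All-cause hospitalization, ED visits and death are collected in both arms from discharge, largely from system records, and a randomized comparison of all-cause events tests net harm without any attribution. This stands. A reader might infer that the plan collects no harms, or that its no-risk statement cannot be tested; the documents support neither. What is missing is any plan to read these events as safety data, and power early on.

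Other points also stand in part:

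- Playback length is approximate, so it is not established that every card has fallen silent before day 38.
- The script sets no end to activity at day 30. The day-45 recall may fall when advised activity is at its highest, so it misses the build-up but not activity as such.
- The card repeats general education given to both arms, and the script defers to contrary advice from a doctor or nurse. Patients who use a cane, walker or wheelchair are excluded, which lowers fall risk.
- The case report forms are not reproduced, so a reason field may already exist. The protocol text describes only the all-cause and HF classes.
- Patients know their arm. A recalled symptom or injury question invites different reporting by group.

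These points lower the likely size of any harm and weaken a recall question. They do not support a categorical denial of risk.

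**Conclusion.** The point holds in a limited form. The risk statement is stronger than the plan can support, early non-serious and activity-related harms have no dedicated capture, and serious events are not planned to be read for safety. Net serious harm can be compared by arm. Power for a 30% relative increase is about 30% to 55% at the 30-day rate, lower by day 14, and 64% to 92% at 180 days for 468 to 968 evaluable patients.

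These figures rest on the plan's expected readmission rates, an assumed 30% increase and, for day 14, a constant hazard. They describe how well readmission data could reveal an excess; they are not an estimate of harm. Nothing in the documents shows that the card is harmful, and for an audio card the matter is one of wording, coding and reporting.

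**What to change.** 1. Record a reason code (HF, fall or injury, faint or arrhythmia, other) for each hospitalization and ED visit already collected. If the forms have such a field, say so in the protocol.
2. Tabulate all-cause hospitalization, ED visits and death by arm at days 14 and 30, with two-sided intervals, and describe them as safety as well as efficacy. The dates are already needed for the time-to-first-event aim. Day 30 is also the time point used to size the trial at 1066, although the listed outcomes are at 45, 90 and 180 days.
3. Replace the no-risk sentence with a statement that risk is expected to be minimal and will be described by group.
4. Optionally, ask both arms at the 45-day call about falls or injuries since discharge, and state that recall is imperfect and that unblinded patients may report differently by arm.
5. The sponsor should reconcile the Physical Activity and Self-Monitoring messages on breathlessness.

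The cost is one form field, two sets of table columns and perhaps one question on an existing call, with no added visit, patient or endpoint. The risk wording becomes less favourable.

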*, secure cards (after developing wording and card designs); identify and train nurses assigned to project; prepare randomization cards/envelopes; ensure hospital-based nurses are trained in human subject protection; receive IRB for approval to conduct the study, receive support for cardiology directors at each hospital and develop database

Timeline, continued													
Work	2017												2018
	Feb	Mar	Apr	May	Jun	Jul	Aug	Sept	Oct	Nov	Dec	Jan	
Patient enrollment and data collection													
Patient 6 month follow-up													
Data entry and cleaning													

Timeline, continued							
Work	2018						
	Feb	Mar	Apr	May	Jun	Jul	Aug
Data entry and cleaning							
Data analysis							
Abstract and presentation preparation/delivery (local stakeholders)							

Abstract submission for national meeting presentation in 2018**							
Prepare paper for publication							

[figure not shown]
**, American Association of Heart Failure Nurses; American Heart Association

V1_01-20-16

NCT02901314

Appendix A; Prototype of Card

Front of Card (Page 1)

Inside of page 1 (left side)

Page 2 (inside of card-right side)

Back of Card (Page 2)

Appendix B. Audio Script

CLEVELAND CLINIC – MY ROAD CARD

Script for American Greetings – Heart Failure

INTRO (plays audio when the card is opened)

Cleveland Clinic cares about you and your health, so we've designed this message to help you take the best care of yourself after leaving the hospital. The messages in this card will cover important information regarding physical activity, diet, medication, and self-monitoring. Your primary medical diagnosis is heart failure. Heart failure is a chronic condition. It is important to take actions to improve your health and stabilize heart failure. Contact your doctor if you still have questions after hearing and carrying out the actions provided in this card.

PHYSICAL ACTIVITY (Plays when the physical activity button is pressed)

Physical activity is extremely important for you. Start slow with walking 10 minutes a day. Over the course of a month, build up to walking 30 minutes a day. Do not worry if you feel short of breath or have a fast heart rate as you engage in physical activity – this is all normal.

Unless your doctor or nurse specifically advised against walking or completing other physical activities you should be active 5 days per week. If you feel ready for more activity beyond walking, you can try swimming, bicycling, or walking briskly.

DIET (Plays when the diet button is pressed)

Eat fresh foods as much as possible. Do not take in more than 2900 mg of sodium per day. Avoid eating frozen, boxed, bagged, or canned foods. The 6 most salty foods are breads, soups, breaded meats, pizza, deli meats and deli sandwiches. Please avoid these salty foods. Limit the use of butter and ask your server about sodium content if you eat at a restaurant. Read food labels for sodium content and serving size to learn if you are taking in too much sodium.

MEDICATIONS (Plays when the medications button is pressed)

Medications are a very important part of heart failure care. They keep your heart from getting bigger and some medications help reduce your heart size and improve your heart's ability to function more normally. Even if you start feeling better, do NOT stop taking your medications. Also, be sure to attend your scheduled office visits so that your medications can be adjusted to the right dose. It is common that a dosing change is needed for 1 or more medications after hospital discharge. Continue taking all of your heart failure medicines as ordered and call your doctor or nurse if you're unsure about anything regarding your medications.

SELF-MONITORING (Plays when the self-monitoring button is pressed)

Weigh yourself every day. If you gain more than 4 pounds unexpectedly, call your doctor or nurse.

Call your doctor or nurse if any you are experiencing any of these other symptoms:

- New or worsening shortness of breath
- New or worsening fatigue or leg weakness
- New or worsening swelling in the ankles and lower legs
- A firm abdomen around your belly button that does not poke inward easily
- An increase or a new need to urinate at night after going to bed
- Needing more pillows at night or needing to sleep in a recliner, and

V1_01-20-16

NCT02901314

- Finding yourself sitting up in bed at night to catch your breath.

V1_01-20-16

NCT02901314

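### The card's activity and self-monitoring messages give opposite instructions for new or worsening breathlessness during activity, so the protocol's absolute no-harm statement is not supported

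*Combined protocol and SAP*

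**What the plan says.** The Intervention section describes a card with a general message that plays on opening and four buttons, each with its own audio. One covers physical activity and another covers signs of worsening (labelled self-monitoring in the script). Patients may replay any button for roughly two weeks, until the battery runs out. Appendix B gives the script.

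- **Physical activity button:** "Do not worry if you feel short of breath or have a fast heart rate as you engage in physical activity", followed by the assurance that "this is all normal".
- **Self-monitoring button:** "Call your doctor or nurse if any you are experiencing any of these other symptoms", with a list that begins "New or worsening shortness of breath".
- **Diet button:** "Do not take in more than 2900 mg of sodium per day".

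On the card's written surface, the Intervention section says that "a nurse can write down the specific dietary sodium limit/day or a phone number". Data Collection says that the "voice-recorded messages are standard care and are not individualized".

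Limitations and Anticipated Problems calls the intervention "a greeting-type card that cannot create harm to patients" and adds that the intervention itself carries no adverse event risk. Under Sample and Setting, enrolled patients have been hospitalized for decompensated heart failure and are in NYHA class III or ambulatory IV.

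**The concern.** Breathlessness is the first symptom on the card's own list of reasons to call, and the activity recording tells patients that breathlessness during activity is normal. A patient may play one button and not the other, and neither recording refers to the other. Someone whose breathlessness on walking has become worse could be reassured by one button and told to call by the other.

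What is at stake is whether a patient recently discharged after decompensation delays a call. The same activity recording asks patients to increase their walking over a month, so exertional symptoms are likely to be something they notice. The protocol treats harm from the card as impossible and so gives no sign that this overlap was considered.

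**Working it through.** No arithmetic applies. The check sets the texts side by side.

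**Step 1: scope of each message.** The activity message is limited by circumstance (during physical activity) but not by whether the symptom is new, worsening or severe. The self-monitoring message is limited by change (new or worsening) but not by circumstance.

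**Step 2: cross the two conditions.**

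| Breathlessness | Activity message | Self-monitoring message | Result |
|---|---|---|---|
| Stable, during activity | do not worry | does not apply | no conflict |
| Stable, at rest | does not apply | does not apply | no conflict |
| New or worsening, at rest | does not apply | call | no conflict |
| New or worsening, during activity | do not worry | call | opposite instructions |

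One cell of four is in conflict. The table counts types of situation and says nothing about how often each occurs.

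**Step 3: does other wording in the script settle that cell?**

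- The activity message yields to a clinician who has advised against walking or other activity. That governs whether to be active, not how to read a symptom.
- The opening message tells patients to contact their doctor if questions remain. A patient told that a symptom is normal may have no question.
- Fast heart rate, also covered by the activity reassurance, is not on the self-monitoring list. The conflict is therefore confined to breathlessness.

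Nothing in the script resolves the fourth cell.

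**Step 4: the no-harm statement.** It is unconditional. It rests on the format (a greeting-type card) and on the content being the same as in usual education. Neither basis addresses two recordings on one card that disagree about a symptom the card itself treats as a reason to call.

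**Step 5: sodium, as a side check.** The recording sets a ceiling of 2900 mg per day. Let W be a limit written on the card by a nurse.

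- W below 2900: a patient who keeps to W satisfies both. There are two figures but no strict contradiction.
- W equal to 2900: no difference.
- W above 2900: an intake between 2900 and W is allowed by the writing and forbidden by the recording.

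The documents give no value of W, do not say how often one would be written, and do not say which figure governs if they differ.

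**The case against.** The strongest reply is that the qualifiers already separate most cases. The activity message speaks only of breathlessness during activity, and the call criterion speaks only of change. That is correct. A reader might infer that the card dismisses breathlessness altogether, but the text does not support this: three of the four situations above are free of conflict. The fourth remains.

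A second reply is that the messages are not what is being tested. The Design section says that the ability to replay them is the intervention, and that the content is standard of care. A reader might infer that the recordings are themselves the intervention and that the conflict therefore biases the readmission comparison. The documents do not support that. On the protocol's account, similar content reaches both groups. The handbook and zones sheet are not reproduced, so it cannot be checked whether the activity sentence is peculiar to the card. The reply does not remove the conflict, because replay repeats whatever the script contains.

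Third, there are mitigations: space on the card for a telephone number, usual discharge teaching in both groups, and prior approval of the script by a senior heart failure clinician. These may reduce the chance of harm. None states how the two messages fit together.

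Fourth, a reader might infer that the sodium figures do contradict each other. They need not. The written limit is offered only as an example of what a provider may add, and a lower one is compatible with a recorded ceiling.

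Fifth, a reader might take the whole card group (281, 441 or 533 patients under Sample Size, depending on where enrolment stops) as the number exposed. Those figures count patients allocated a card. The protocol itself acknowledges that some may never listen after discharge.

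**Conclusion.** The point holds in a narrow form. For new or worsening breathlessness during activity, two separately played recordings on the same card give opposite instructions, and the script has no wording that reconciles them. The absolute statement that the card cannot cause harm is therefore not supported. This does not show that harm is likely, nor that a minimal-risk classification is wrong.

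The clinical effect cannot be sized from the documents, and no effect on the comparison between groups is shown. The sample size, error rate and analysis are untouched. The point deserves action because it concerns patient safety in NYHA class III or ambulatory IV heart failure and is inexpensive to correct. The sodium limits are a minor note: a possible inconsistency with no rule for resolving it.

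The conclusion assumes that the recorded audio follows Appendix B and that no printed text on the card clarifies the messages. The card images in Appendix A are not shown in the text reviewed, so the second assumption could not be checked.

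**What to change.** 1. Before recording, have the script's clinical approvers reconcile the physical activity message with the self-monitoring call criteria, so that each can be played alone without contradicting the other. What the wording should say is for those clinicians.
2. In Limitations and Anticipated Problems, remove the absolute statement that the card cannot cause harm, together with the companion statement that the intervention carries no adverse event risk. Replace them with an assessment that acknowledges the content of the messages.
3. As a minor edit, reconcile the Intervention section with the diet script by stating which sodium limit governs if a handwritten one differs from the recorded one. This review takes no position on the figure.

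The cost is a short script edit and a protocol text change. The timeline lists securing the cards, once wording and design are settled, as start-up work, so the edit belongs there. If cards have already been recorded, the cost is a re-recording or a printed insert.
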